Figure 3	Images of Mid-Vessel Segment Explanted at 11-Months Post-Implant	35

List of Abbreviations

ADR	Adverse drug reaction
AE	Adverse event
ALT	Alanine transaminase
AST	Aspartate transaminase
AV	Arteriovenous
AVF	Autologous arteriovenous fistula
BUN	Blood urea nitrogen
CDC	Center for Disease Control and Prevention
CEC	Clinical Events Committee
CKD	Chronic kidney disease
CRO	Contract research organization
CVC	Central venous catheter
D	Day
DHHS	Department of Health and Human Services
DMC	Data Monitoring Committee
DTH	Delayed-type Hypersensitivity
ECG	Electrocardiogram
ECM	Extracellular Matrix
eCRF	Electronic case report form
ePTFE	Expanded polytetrafluoroethylene
ESA	Erythropoiesis-stimulating agent
ESRD	End-stage renal disease
ET	Early termination
GCP	Good Clinical Practice
GLP	Good Laboratory Practice
HAV	Human acellular vessel (note was HAVG [Human Acellular Vascular Graft])
HbA1c	Hemoglobin A1c
ICH	International Conference on Harmonization
ICMJE	International Committee of Medical Journal Editors
IEC	Independent ethics committee
IgG	Immunoglobulin G
IMP	Investigational medicinal product

List of Abbreviations

IMPD	Investigational medicinal product dossier
IND	Investigational new drug
INR	International normalized ratio
IRB	Institutional Review Board
ISO	International Organization for Standardization
ITT	Intent-to-Treat
LMWH	Low molecular weight heparin
M	Month
MedDRA	Medical Dictionary for Regulatory Activities
mlITT	Modified Intent-to-Treat
PAD	Peripheral arterial disease
PE	Physical examination
PHI	Protected health information
PP	Per Protocol
PRA	Panel reactive antibody
PT	Prothrombin time
PTFE	Polytetrafluoroethylene
RBC	Red blood cell
RRT	Renal replacement therapy
SAE	Serious adverse event
SOP	Standard operating procedure
spKt/V _{urea}	Measure of dialysis adequacy for a single hemodialysis treatment using the single pooled method
SUSAR	Suspected unexpected serious adverse reaction
ULN	Upper limit of normal
US	United States
WBC	White blood cell

Protocol Summary

Full Title	An Assessment of Humacyte's Human Acellular Vessel in Patients Needing Renal Replacement Therapy: A Comparison with ePTFE Grafts as Conduits for Hemodialysis (HUMANITY)
Clinical Trial Phase	Phase 3
Sponsor	Humacyte, Inc.
Planned Study Sites	Approximately 35 Sites in the US, Europe and Israel
Sample Size	At least 350 evaluable subjects with implanted study conduits; 175 with Human Acellular Vessel (HAV), 175 with an expanded polytetrafluoroethylene (ePTFE) graft
Expected Enrollment Start	2Q2016
Study Population	Subjects with end-stage renal disease (ESRD) who require hemodialysis and are targeted for implantation of an arteriovenous (AV) graft for dialysis access.
Enrollment Period	16 months
Study Duration	Each subject will be followed by study specific visits until he/she completes 2 years (24 months) of follow-up after implantation (irrespective of patency status). After 2 years, only subjects with a patent study conduit will be followed (while the study conduit remains patent) for up to 5 years (60 months) post-implantation at routine study visits. The expected duration of the clinical investigation is 76 months (initiation of enrollment through completion of data collection).
Study Design	Prospective, multicenter, multinational, open-label, randomized, two-arm, comparative study.
Investigational Device/Intervention Description	
The Investigational Medicinal Product (IMP) is Humacyte's HAV, which is a tissue-engineered vascular conduit for hemodialysis access. The comparators are one of the following commercially available 6 mm ePTFE grafts:
 
• Gore® PROPATEN® Vascular Graft (6mm x 40cm, straight, standard wall, non-stretch, non- tapered)• Bard® Impra® Vascular Graft (6mm x 40cm, straight, standard wall, non-stretch, non- tapered)

	
Subjects will be implanted with either a HAV or an ePTFE graft in the forearm or upper arm using standard vascular surgical techniques.
 
The randomization will occur during surgery and be 1:1 and stratified by upper arm or forearm placement based on the Principal Investigator's determination of where the study conduit should be located.
 
All subjects will be required to take daily aspirin (75 to 325 mg) unless they are already taking another antiplatelet agent. Aspirin should be initiated no later than the day after surgical implantation of the study conduit (Day 1). If low molecular weight heparin (LMWH) is administered post-operatively, aspirin or other antiplatelet agent should be initiated after stopping LMWH.
 
Subjects who are known to be aspirin-sensitive should take another antiplatelet agent at the discretion of the Principal Investigator.

Objectives	
Primary Objective	To compare the Secondary Patency of the HAV with that of the ePTFE graft when used as a conduit for hemodialysis.
Secondary Objectives	
Key Secondary Objectives	
Efficacy
 
To compare the Primary Patency of the HAV with that of the ePTFE graft.
 
Safety
 
To compare the rate of access-related infections for the HAV with that of the ePTFE graft.

Other Secondary Objectives	
Efficacy
 
1. To compare the rate of interventions needed to maintain/restore patency of the HAV with that of the ePTFE graft.2. To compare the Primary Assisted Patency of the HAV with that of the ePTFE graft.3. To describe the histopathological remodeling of samples from HAVs and ePTFE grafts.4. To compare the efficiency of dialysis with the HAV with that of

	
the ePTFE graft in a subset of subjects.
 
Safety
 
1. To compare the safety and tolerability of the HAV with that of the ePTFE graft.2. To compare the relative rates of true aneurysm and pseudo-aneurysm formation.
Inclusion Criteria	
1. Subjects with ESRD who are not, or who are no longer, candidates for creation of an autologous AV fistula and therefore need placement of an AV graft in the arm (upper- or forearm) to start or maintain hemodialysis therapy.2. Either on hemodialysis or expected to start hemodialysis within 12 weeks of study conduit implantation.3. At least 18 years of age at Screening.4. Suitable anatomy for implantation of straight or looped conduits in either the forearm or upper arm (not crossing the elbow).5. Hemoglobin ≥ 8 g/dL and platelet count $\geq 100,000$ cells/mm³ prior to Day 0 (within 35 days).6. Other hematological and biochemical parameters within a range consistent with ESRD prior to Day 0 (within 35 days).7. Adequate liver function prior to Day 0 (within 35 days), defined as both of the following:
a. ≤ 2 times upper limit of normal (ULN) for serum bilirubin, aspartate transaminase (AST), and alanine transaminase (ALT)b. ≤ 1.5 for International Normalized Ratio (INR) or prothrombin time (PT) ≤ 18 seconds unless the subject is taking an anticoagulant at the time8. Female subjects must be either:
a. Of non-childbearing potential, which is defined as post-menopausal (at least 1 year without menses prior to Screening) or documented surgically sterile or post hysterectomy (at least 1 month prior to Screening)b. Or, of childbearing potential, in which case:
i. Must have a negative serum or urine

	
pregnancy test at Screening, and
 
ii. Must agree to use at least one form of the following birth control methods for the duration of the study:
 
1. Established use of oral, injectable or implanted hormonal methods of contraception2. Placement of an intrauterine device or intrauterine system3. Barrier methods of contraception: condom or occlusive cap (diaphragm or cervical/vault caps) with spermicidal foam/ gel/ film/ cream/ suppository 
9. Subject, or legal representative, able to communicate effectively with investigative staff, competent and willing to give written informed consent, and able to comply with entire study procedures including all scheduled follow-up visits.
 
10. Life expectancy of at least 1 year.

Exclusion Criteria	
1. History or evidence of severe peripheral vascular disease in the intended arm for implantation.2. Known or suspected central vein stenosis or conduit occlusion on the ipsilateral side of the planned implantation, unless the stenosis is corrected prior to study conduit implantation.3. Treatment with any investigational drug or device within 60 days prior to study entry (Day 0) or ongoing participation in a clinical trial of an investigational product.4. Cancer that is actively being treated with a cytotoxic agent.5. Documented hyper-coagulable state.6. Bleeding diathesis.7. Active clinically significant immune-mediated disease, not controlled by maintenance immunosuppression.
a. Low dose glucocorticoid therapy (e.g. up to 10mg a day prednisone or prednisolone) is acceptable.b. High dose glucocorticoid therapy for treatment of autoimmune flare, or other inflammatory diseases is excluded.c. Patients using glucocorticoids for

	
immunosuppression post-transplant to prevent against transplanted allograft rejection in the period post allograft failure are excluded.
 
d. The following examples of immunosuppressive agents (or the like) are exclusionary for enrollment in this clinical trial:
 
i. tacrolimus or FK506 [Prograf]ii. mycophenolate mofetil [Cellcept],iii. cyclosporine [Sandimmune or Gengraf]iv. Sirolimus administered systemically (Sirolimus in drug eluting stents is NOT an exclusion) 
8. Anticipated renal transplant within 6 months.
 
9. Venous outflow from study conduit cannot be placed more centrally than the venous outflow of any previous failed access in that extremity.
 
10. Active local or systemic infection (white blood cells [WBC] > 15,000 cells/mm³ at Screening). If the infection resolves, the subject must be at least one week post resolution of that infection before implantation.
 
11. Known serious allergy to planned antiplatelet agent.
 
12. Pregnant women, or women intending to become pregnant during the course of the trial.
 
13. Any other condition which in the judgment of the investigator would preclude adequate evaluation of the safety and efficacy of the study conduit.
 
14. Previous enrollment in this study or any other study with the HAV.
 
15. Employees of Humacyte and employees or relatives of the investigator.

Criteria for Evaluation	
Primary Endpoint	Time to loss of Secondary Patency from implantation 
• Defined as 'the interval from the time of access placement until access abandonment', i.e., patent with or without interventions. (Sidawy 2002)
Secondary Endpoints	

Key Secondary Endpoints	
Efficacy
 
Time to loss of Primary Patency from implantation
 
Defined as 'the interval from the time of access placement until any intervention designed to maintain or reestablish patency, access thrombosis or the time of measurement of patency', i.e., patent without interventions (Sidawy 2002). 
Safety
 
Access-related infections (CDC 2013).

Other Secondary Endpoints	
Efficacy
 
Rate of interventions required to achieve/maintain Secondary Patency.Time to loss of Primary Assisted Patency from implantation.
Defined as 'the interval from the time of access placement until access thrombosis or the time of measurement of patency, including intervening manipulations (surgical or endovascular interventions) designed to maintain the functionality of patent access' i.e., patent without an intervention to clear a thrombus (Sidawy 2002).Histopathological remodeling of any study conduit (based on any samples collected).The efficiency of dialysis as assessed by $spKt/V_{urea}$ (obtained from dialysis unit for a subset of subjects). 
Safety
 
Frequency and severity of adverse events (AEs)Study conduit dilatation:
True aneurysm formation (conduit lumen diameter > 9 mm)Pseudo-aneurysm formationStudy conduit spontaneous ruptureAnastomotic bleeding or spontaneous rupture

	
Events of Special Interest
 
Events of Special Interest related to interventions and infections will be evaluated and include the following:
 
• Study conduit abandonment• Thrombosis / thrombectomy• Angioplasty or stenting• Access-related infection• Pseudo-aneurysm or true aneurysm (conduit lumen diameter >9 mm) formation• Study conduit spontaneous rupture
◦ Iatrogenic injuries are not an Event of Special Interest and should be reported as an AE• Revision or ligation of the study conduit• Study conduit removal• Steal syndrome
Data Analysis	
Populations	
The Intent-to-Treat (ITT) population is defined as all randomized subjects (based on study conduit group assignment).
 
The modified Intent-to-Treat (mITT) population is defined as all subjects in whom a study conduit has been implanted (based on actual conduit implanted).
 
The Per Protocol (PP) population is defined as all subjects in whom a study conduit has been implanted (based on actual conduit implanted) and in whom there were no major protocol violations.

Primary Efficacy Analysis	
The primary efficacy analysis will be a non-inferiority analysis, which will be conducted when all subjects are at least 18 months post-implantation. It will be conducted using the ITT population with confirmatory analyses in the mITT and PP populations.
 
The following rules for the analysis will apply:
 
• Subjects in whom the wrong study conduit was implanted (e.g., an HAV implanted in a subject randomized to an

	
ePTFE graft) will be analyzed within their randomized group rather than in their implanted group.
 
Subjects in whom no study conduit was implanted will be considered as if abandoned on Day 0 and included in their randomized group. 
The following censoring rules will apply to all 'time to' analyses:
 
Subjects who have patent study conduits at the time of death, kidney transplant or withdrawal will be censored at that timepoint.Subjects who are lost to follow-up will be censored at their last visit when it was known that the study conduit was patent.Subjects in whom a delayed decision is made to abandon the study conduit (e.g., delayed and then failed thrombectomy) will have the date of abandonment set as the date of the initial recognition of the thrombosis, not the date that a final decision was made. 
The hazard ratio (HAV relative to ePTFE) will be estimated using a Cox proportional hazards regression model with treatment group and the randomization stratification variable as factors. Based on the estimated 18-month event-free rate in the ePTFE arm, the non-inferiority margin will be determined by the hazard ratio corresponding to a difference of 10 percentage points. If the lower limit of the two-sided 95% confidence interval for the hazard ratio is greater than the corresponding non-inferiority bound, then non-inferiority will be demonstrated.

Secondary Efficacy Analyses	
Key Secondary Analysis Efficacy	
If the primary efficacy analysis demonstrates non-inferiority, the following key secondary analyses will be completed at the same timepoint in the ITT population using a fixed sequence testing procedure to control the overall level of significance. Thus, the results of a given key secondary analysis will be considered confirmatory only if the results of all previous tests are successful based on the use of a two-sided test at the alpha=0.05 level of significance. However, once a non-successful result is obtained, all subsequent results will be considered as exploratory rather than confirmatory. The key secondary analyses are the following:
 
Superiority analysis of the time to loss of Secondary

	
Patency;
 
• Non-inferiority analysis of the time to loss of Primary Patency;• Superiority analysis of the time to loss of Primary Patency. 
The non-inferiority analysis of time to loss of Primary Patency will be completed using the same statistical approach and non-inferiority margin as specified for the primary analysis.
 
The superiority analyses will be completed using the same statistical model as described for the corresponding non-inferiority analysis. The two arms will be compared using a two-sided test at the alpha=0.05 level of significance.
 
In order to provide descriptive summary statistics that are of interest, point estimates and 95% confidence intervals for patency (Primary, Primary Assisted and Secondary) survival probabilities will be provided for each group at 6, 12, 18, and 24 months. These estimates will be computed from Kaplan-Meier survival curves for each treatment group for each of the endpoints.

Key Secondary Analysis Safety	
For each of the two treatment groups, the access-related infection rate will be computed in 2 ways:
 
• Rate of access-related infections per 100 person-years of HAV/ePTFE use (i.e., censored at abandonment).• Rate of access-related infections per 100 person-years over the 2-year post-implantation follow-up period. 
These analyses will be based on adjudicated events using a standardized definition of access-related infections (CDC 2013).
 
For each of the 2 definitions, the infection rates in the two arms will be compared using a Poisson regression model with treatment group and the randomization stratification variable as factors. This analysis will be conducted using a two-sided test at the alpha=0.05 level of significance.

Other Secondary Analysis Efficacy	
In the primary and key secondary analyses of Primary Patency and Secondary Patency, death will be treated as a censored outcome. These analyses will be repeated as supportive analyses with death treated as an event. Additionally, a time to event analysis will be conducted for all censored subjects and any subjects who withdraw for any reason.
 
All secondary efficacy analyses that are superiority comparisons will

	
be carried out using two-sided tests at the alpha=0.05 level of significance, with no adjustment for multiplicity.
 
The rates of interventions (number of interventions per 100 person-years) in the two arms will be compared using a Poisson regression model with treatment group and the randomization stratification variable as factors.
 
Secondary endpoints that are defined as time-to-event variables will be summarized using the Kaplan-Meier method and analyzed using the log-rank test. Proportion endpoints will be analyzed using Pearson's chi-square test and all other quantitative endpoints will be analyzed using the two-sample t-test.
 
Any analysis on histopathological remodeling of any study conduit will be descriptive only.

Other Secondary Analysis Safety	All other safety data will be described only (i.e., no inferential statistics).
Sample Size	
The original sample size calculation was based on the following assumptions:
 
For the primary endpoint of time to loss of Secondary Patency, the assumed 12-month event-free rate in the ePTFE arm is 60%. Based on 1:1 randomization, an estimated 16-month enrollment period, and a 12-month follow-up period, a total sample size of 350 subjects will provide:
 
• 90% power to demonstrate non-inferiority (non-inferiority margin=10%) if the 12-month event-free rate in the HAV arm is 66%• 90% power to demonstrate superiority if the 12-month event-free rate in the HAV arm is 76% 
For the key secondary endpoint of time to loss of Primary Patency, the assumed 6-month event-free rate in the ePTFE arm is 50%.
 
Based on 1:1 randomization, a 16-month enrollment period, and a 12-month follow-up period, and under the assumption that the true 6-month event-free rate in the HAV arm is 55%, a total sample size of 350 subjects will provide greater than 90% power to demonstrate non-inferiority. If the true rate in the HAV arm is as low as 53%, then there will be greater than 80% power to demonstrate non-inferiority.

	
During the course of the study a high enrolling site (~10% of total subjects) early terminated all of their remaining subjects and withdrew from study participation. The majority of these subjects had not yet had an event that would contribute to the primary endpoint analysis. To mitigate the potential loss of study power from this unexpected situation, the decision was made to extend the follow-up period for the primary and secondary efficacy analyses from 12 months post-implant to 18 months post-implant.

Data Monitoring Committee (DMC)	
A Data Monitoring Committee (DMC) will be established to review safety on an ongoing basis and to provide recommendations about stopping, continuing or otherwise modifying the study. As part of their oversight of study conduct, the DMC will review the pattern of interventions and abandonments between treatment groups overall and by study site to assess whether the management of access complications is similar in the two treatment groups. Responsibilities of the DMC will include review of aggregate safety data from other studies in the HAV clinical development program.
 
The DMC will consist of individuals who are not directly involved in the conduct of the study. A separate charter will be established that will describe the roles and responsibilities of the DMC.

Clinical Events Committee (CEC) (Adjudication Process)	
A Clinical Events Committee (CEC) will be established to do the following:
 
• Prospectively provide to study sites a set of clinical guidelines for study conduit interventions and abandonment.• Review study conduit interventions and abandonment in a blinded fashion to assess compliance with provided guidelines.• Adjudicate study conduit revisions to determine whether the original study conduit was still being used for dialysis.• Adjudicate access-related infections using the Centers for Disease Control and Prevention (CDC) definitions for dialysis-associated infections (CDC 2013). 
The CEC will consist of individuals who are not directly involved in the conduct of the study. A separate charter will be established that will describe the roles and responsibilities of the CEC.

Protocol Approval (Version and Date)	v5.0 08 August 2018
---	---------------------

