10.3.3 Key Secondary Efficacy Analyses

If the primary efficacy analysis demonstrates non-inferiority, the following key secondary analyses will be completed at the same timepoint in the ITT population using a fixed sequence testing procedure to control the overall level of significance. Thus, the results of a given key secondary analysis will be considered confirmatory only if the results of all previous tests are successful based on the use of a two-sided test at the alpha=0.05 level of significance. However, once a non-successful result is obtained, all subsequent results will be considered as exploratory rather than confirmatory. The key secondary analyses are as follows:

- Superiority analysis of the time to loss of Secondary Patency
- Non-inferiority analysis of the time to loss of Primary Patency
- Superiority analysis of the time to loss of Primary Patency

The non-inferiority analysis of time to loss of Primary Patency will be completed using the same statistical approach and non-inferiority margin as specified for the primary analysis.

The superiority analyses will be completed using the same statistical model as described for the corresponding non-inferiority analysis. The two arms will be compared using a two-sided test at the alpha=0.05 level of significance.

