10.5 Sample Size

The original sample size calculation was based on the following assumptions:

For the primary endpoint of time to loss of Secondary Patency, the assumed 12-month event-free rates in the ePTFE arm is 60%. Based on 1:1 randomization, a 16-month enrollment period, and a 12-month follow-up period, a total sample size of 350 subjects will provide:

- 90% power to demonstrate non-inferiority (non-inferiority margin=10%) if the 12-month event-free rate in the HAV arm is 66%
- 90% power to demonstrate superiority if the 12-month event-free rate in the HAV arm is 76%

For the key secondary endpoint of time to loss of Primary Patency, the assumed 6-month event-free rate in the ePTFE arm is 50%. Based on 1:1 randomization, a 16-month enrollment period, and a 12-month follow-up period, and under the assumption that the true 6-month event-free rate in the HAV arm is 55%, a total sample size of 350 subjects will provide greater than 90% power to demonstrate non-inferiority. If the true rate in the HAV arm is as low as 53%, then there will be greater than 80% power to demonstrate non-inferiority.

During the course of the study a high enrolling site (~10% of total subjects) early terminated all of their remaining subjects and withdrew from study participation. The majority of these subjects had not yet had an event that would contribute to the primary endpoint analysis. To mitigate the potential loss of study power from this unexpected situation, the decision was made to extend the follow-up period for the primary and secondary efficacy analyses from 12 months post-implant to 18 months post-implant.

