### **5.4 BASELINE CHARACTERISTICS**

Baseline characteristics, including duration of end-stage renal disease, number of previous conduits placed with a description of what they were, etc. will be summarized using the ITT analysis set for each treatment group as well as for all subjects. Categorical variables will be summarized using frequencies and percentages and continuous measures will be summarized using the number of non-missing observations, mean, standard deviation, and possibly other descriptive statistics. No formal hypothesis testing will be performed to compare differences in baseline characteristics between treatment groups. A by-subject baseline characteristics listing will be provided.

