## **6.5 PROGNOSTIC FACTORS AND SUBGROUP ANALYSES**

No analyses based on prognostic factors are planned for the study. Sub-group analysis by geographic region (USA versus non-USA), gender, race (White; non-White), ethnicity (Hispanic or Latino; non-Hispanic or Latino) actual surgical location (upper arm; forearm), age group (<55; >=55 and <=70; >70), BMI (<30; >=30) will be performed. The subgroup analyses will be performed by repeating the statistical methods described above for loss of secondary patency and loss of primary patency for each subgroup, except that the models will be adjusted by the actual surgical placement location (upper arm, forearm). For example, the models will be performed including only male subjects, and then will be repeated including only female subjects.

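### The two superiority tests adjust only for arm placement; prespecified adjustment for baseline data already recorded is a cheap, modest power gain rather than the repair of an error

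*Protocol*

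**What the plan says.** Protocol 10.3.2 specifies a "Cox proportional hazards regression model with treatment group and the randomization stratification variable as factors". SAP 6.1 names that variable as surgical placement, and SAP 3.2.1 leaves country out of the effect analysis. Protocol 10.3.3 carries the model over to superiority: "The superiority analyses will be completed using the same statistical model as described for the corresponding non-inferiority analysis", and "The two arms will be compared using a two-sided test at the alpha=0.05 level of significance". SAP 6.2 says the same in its own terms.

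Superiority of Secondary Patency is the first key secondary test after the primary non-inferiority test. If it fails, both Primary Patency tests become exploratory.

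SAP 6.5 states: "No analyses based on prognostic factors are planned for the study". The baseline data are collected all the same. Protocol 8.1.2 and 8.1.3 record age, gender, cause of renal failure, dialysis history and past access procedures. SAP 5.4 summarises, among other items, "number of previous conduits placed with a description of what they were". In the SAP these variables feed descriptive tables, and some of them (age, gender, race, BMI) define subgroups.

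**The concern.** Leaving a prognostic covariate out of a Cox model pulls the estimated treatment hazard ratio toward 1, with almost no change in its standard error. The test therefore loses power. The loss grows with the strength of the covariate and with the share of subjects who have the event, so it should be larger for Primary than for Secondary Patency. Protocol 2.4.1 aims for a broad ESRD population, so baseline risk may well vary.

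Two features of the plan make the power of this test matter. The first superiority test gates everything after it. The sponsor also treated power as a live issue: follow-up was extended from 12 to 18 months after a site with about 10% of subjects withdrew.

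**Working it through.** **Inputs from the documents.** 350 subjects, 1:1; 16-month accrual; two-sided alpha 0.05; Secondary Patency 60% (ePTFE) v 76% (HAV) at 12 months with 90% power for superiority; Primary Patency 50% (ePTFE) at 6 months with 55% or 53% (HAV), given for non-inferiority only (Protocol 10.5, SAP 11). Analysis at 18 months minimum follow-up (Protocol 10.3.2). Deaths of about 20% per year, censored (SAP 6.1).

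**Assumptions.** Exponential event times. One normally distributed baseline risk score with log-hazard SD 0, 0.3, 0.5 or 0.7 (hazard ratio per SD 1.00, 1.35, 1.65, 2.01). The effects 72% v 60% and 60% v 50% are also assumptions. The loss of the withdrawn site is not modelled.

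**Step 1: the plan's own figure.** HR = ln 0.76 / ln 0.60 = 0.537, so |ln HR| = 0.621. With 12 months per subject and no dropout, events = 175 × (0.40 + 0.24) = 112. Schoenfeld power = Φ(√(112/4) × 0.621 − 1.96) = Φ(1.33) = 90.8%. The stated 90% is reproduced with no baseline covariates.

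**Step 2: the current design.** Monthly death hazard c = −ln 0.8 / 12 = 0.0186. The event probability λ/(λ+c) × [1 − exp(−(λ+c)t)] is averaged over t from 18 to 34 months. With no prognostic score:

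| Comparison | HR | Events | Power |
|---|---|---|---|
| Secondary 76% v 60%, 12 months | 0.537 | 159 | Φ(√(159/4) × 0.621 − 1.96) = 97.5% |
| Secondary 72% v 60%, 12 months (assumed) | 0.643 | 168 | Φ(√(168/4) × 0.442 − 1.96) = 82% |
| Primary 60% v 50%, 6 months (assumed) | 0.737 | 278 | Φ(√(278/4) × 0.305 − 1.96) = 72% |
| Primary 55% v 50%, 6 months | 0.863 | 285 | Φ(√(285/4) × 0.148 − 1.96) = 24% |

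**Step 3: simulation with and without the score.** Design as in step 2, with arm-level event-free rates held at the stated values; 2,000 to 3,000 trials per cell, simulation error about 1 point or less. In the 72% v 60% and 60% v 50% columns the adjusted model also carries four pure-noise covariates, to mimic a list in which some items do not predict. Power (%), unadjusted → adjusted:

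| SD of score | Secondary 76 v 60 | Secondary 72 v 60 (assumed) | Primary 60 v 50 (assumed) |
|---|---|---|---|
| 0 | 97.2 → 97.2 | 82.5 → 82.6 | 70.5 → 70.6 |
| 0.3 | 97.5 → 98.0 | 79.8 → 81.6 | 70.0 → 74.1 |
| 0.5 | 96.6 → 98.1 | 77.7 → 83.2 | 64.1 → 75.2 |
| 0.7 | 95.2 → 98.6 | 76.2 → 86.2 | 62.7 → 81.2 |

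For Primary Patency at the documented 55% v 50%, power is about 21% unadjusted and 23% to 30% adjusted over SD 0.3 to 0.7. With no treatment effect, rejection is 4.4% to 5.4% unadjusted and 4.5% to 5.9% adjusted (simulation error about 0.5 points).

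**Step 4: where the gain comes from.** At 76% v 60% and SD 0.5, adjustment moves the average HR from 0.546 to 0.519, while its standard error goes from 0.166 to 0.167. The adjusted HR is a conditional quantity, not a more precise estimate of the same one.

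**Step 5: why non-inferiority must keep its model.** The margin comes from unadjusted Kaplan-Meier rates: ln 0.50 / ln 0.60 = 1.357 if ePTFE is 60%. At a true 10-point deficit the conditional HR is 1.389 (SD 0.5) or 1.486 (SD 1.0). An adjusted HR would be compared with a margin on a different scale. Superiority has no such problem, because a null HR of 1 is the same on both scales.

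**The case against.** The strongest reply is that nothing here is wrong. Adjusting only for the placement stratum is prespecified and controls type I error, and the stated superiority power is met without further covariates. That stands.

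The benefit also rests entirely on an assumed prognostic strength, and the larger gains need treatment effects that the documents do not give. That stands too. A reader might infer that the superiority tests are underpowered as planned, or that some 20 points of power are being lost. The documents do not support either: at the plan's own effect, power is 95% or more and the gain is at most about 3 points. For Primary Patency there is no stated superiority effect or power to fall short of, and at 55% v 50% adjustment would not rescue the test.

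A third point is that the change is not free. One model now gives one hazard ratio and one interval for both non-inferiority and superiority. After the change there would be two for the same endpoint, with different meanings. Choosing covariates late in an open-label trial also invites doubt; the current SAP already revises a version dated 01May2019.

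Finally, baseline catheter status is an obvious candidate covariate, but it is not shown as a Screening or Day 0 item. The catheter-use row in Protocol Appendix 1 starts at Day 7-15, and Protocol 8.5.2.2 records only the removal of a catheter present before randomisation.

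What survives the reply is narrower. If the true effect lies below 16 points, power is not near its ceiling. Prespecified adjustment then helps if the covariates predict, and costs essentially nothing in power if they do not.

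**Conclusion.** This is an optional efficiency improvement. Both superiority models omit baseline data that the trial already records, so some power may be given up; how much cannot be known from the documents. Over an assumed score SD of 0.3 to 0.7 the gain is:

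- about 0.5 to 3.4 points for Secondary Patency at 76% v 60%;
- about 2 to 10 points for Secondary Patency at an assumed 72% v 60%;
- about 4 to 18 points for Primary Patency at an assumed 60% v 50% at 6 months;
- a move from about 21% to 23-30% for Primary Patency at 55% v 50%.

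At SD 0 there is no gain. The figures assume exponential event times, 20% annual deaths as the only dropout, and a score that the chosen covariates capture fully; a real list would capture less.

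**What to change.** In Protocol 10.3.3 and SAP 6.2, fit only the two superiority Cox models with treatment, arm placement and a short fixed list recorded before randomisation: age, sex, number of previous accesses, and on dialysis at implantation. Use a missing-value indicator so that no subject drops out. Add baseline catheter status only if it is confirmed as a pre-randomisation field.

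Fix the list before any arm-level results are seen. If they have been seen, the adjusted test can be supportive only.

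Keep the present model for both non-inferiority tests, and report the unadjusted superiority hazard ratio as supportive.

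The cost is SAP wording, a matching protocol sentence and a few lines of code, with no new data. The report must explain that the superiority hazard ratio is conditional on the covariates and will differ from the non-inferiority hazard ratio for the same endpoint.
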